5.5.9.1.5. Laboratory Tests

The incidence rates of patients with treatment-emergent abnormal, high, or low laboratory values for each laboratory test based on Covance reference ranges at any time postbaseline will be summarized. The baseline and postbaseline definitions are summarized in [Table CGAM.5.3](#). The treatment comparisons will be assessed using Fisher's exact tests for SP III.

Patients will be defined as having a treatment-emergent low value if they have all normal or high values at baseline, followed by a value below the lower reference limit at any postbaseline visit. Patients with all normal or high values at baseline (no low values) will be included in the analysis of treatment-emergent low laboratory values. Patients will be defined as having a treatment-emergent high value if they have all normal or low values at baseline, followed by a value above the upper reference limit at any postbaseline visit. Patients with all normal or low values at baseline (no high values) will be included in the analysis of treatment-emergent high laboratory values.

For analytes simply classified as normal or abnormal, patients will be defined as having a treatment-emergent abnormal value if they have all normal values at baseline, followed by an abnormal value at any postbaseline visit. Patients with all normal values at baseline will be included in the analysis of treatment-emergent abnormal laboratory values.

The incidence of patients with the following elevations in hepatic laboratory tests at any time postbaseline will also be summarized, and comparison between treatment groups will be done for SP III using Fisher's exact test.

- The percentages of patients with an alanine aminotransferase (ALT) or aspartate aminotransferase (AST) measurement greater than or equal to 3 times (3 \times), 5 times (5 \times), and 10 times (10 \times) the Covance upper limit of normal (ULN) during the treatment period will be summarized for all patients with a postbaseline value.
- The percentages of patients with an alkaline phosphatase (ALP) greater than or equal to 2 times (2 \times) the Covance ULN during the treatment period will be summarized for all patients with a postbaseline value.
- The percentages of patients with a total bilirubin (TBIL) measurement greater than or equal to 2 times (2 \times) ULN during the treatment period will be summarized for all patients with a postbaseline value.

The analysis of elevation in ALT, AST, ALP and TBIL will contain 3 subsets:

- patients whose nonmissing maximum baseline value is less than or equal to 1 \times ULN for ALT, AST, ALP, and TBIL.
- patients whose nonmissing maximum baseline value is greater than 1 \times ULN for ALT, AST, ALP, and TBIL, and at the same time less than or equal to 2 \times ULN for ALT and AST, 1.5 \times ULN for ALP and TBIL.
- patients whose nonmissing maximum baseline value is greater than 2 \times ULN for ALT and AST, 1.5 \times ULN for ALP and TBIL.

A listing of patients who had met any following criteria postbaseline will be provided over all study phases: ALT \geq 3 \times ULN, or AST \geq 3 \times ULN, or ALP \geq 2 \times ULN, or TBIL \geq 2 \times ULN.

5.5.9.1.6. *Immunogenicity*

In the immunogenicity assay process, each sample is potentially examined multiple times, according to a hierarchical procedure, to produce a sample ADA assay result and potentially a sample NAb assay result. The cut points used, the drug tolerance of an assay, and the possible values of titers are operating characteristics of the assay.

It can be the case that the presence of high concentrations of galcanezumab will affect the measurements of the presence of ADA or NAb, and conversely high levels of ADA or NAb may affect the measurement of GMB concentration. Thus an GMB drug concentration, assessed from a sample drawn at the same time as the ADA sample, plays a key role in clinical interpretation of a sample when the laboratory result is Not Detected.

5.5.9.1.6.1. Definitions of Sample ADA Status

[Table CGAM.5.8](#) and [Table CGAM.5.9](#) list sample ADA assay results and clinical interpretation of the sample results.

Table CGAM.5.8. Sample ADA Assay Results

Sample Laboratory Result	Explanation
Detected	ADA are detected and confirmed.
Not Detected	The raw result as reported from the laboratory indicates not detected. The clinical interpretation of such results depends other factors (see below).
NO TEST, QNS, etc.	Sample exists but was unevaluable by the assay.

Abbreviation: ADA = anti-drug antibody.

Table CGAM.5.9. Sample Clinical ADA Interpretation Results

Sample Clinical Interpretation	Explanation
ADA Present	ADA assay result is Detected
ADA Not Present	ADA assay result is Not Detected and simultaneous drug concentration is at a level that has been demonstrated to not interfere in the ADA detection method (ie, drug concentration is below the assay's drug tolerance level). For patients receiving placebo, drug concentration is not assessed and is assumed to be below the assay's drug tolerance level.
ADA Inconclusive	ADA assay result is Not Detected but drug concentration in the sample is at a level that can cause interference in the ADA detection method.
ADA Not Detected with Drug Concentration Not Available	If drug concentration analysis was planned but result is not available for a treatment-period sample, a Not Detected sample will be declared ADA Not Detected with Drug Concentration Not Available. In the computation of Patient ADA status (see below, Section 5.5.9.1.6.2), these samples will be considered ADA Not Present, on the basis of prior knowledge that the drug tolerance level of the ADA assay is high relative to the expected drug concentration levels.
ADA Missing	ADA sample not drawn, QNS, not tested, etc., causing there to be no laboratory result reported or the result is reported as "no test".

Sample Clinical ADA Interpretation Results (Abbreviation)

Abbreviation: ADA = anti-drug antibody.

Parallel terminology applies for NAb Detected, NAb Not Detected, NAb Present, NAb Not Present, NAb Inconclusive, NAb Not Detected with Drug Concentration Not Available, and NAb Missing. Anti-drug antibodies and NAb are distinct assays and have different assay operating characteristics.

5.5.9.1.6.2. Definitions of Patient ADA Status

Patient evaluable for TE ADA: A patient is evaluable for TE ADA if the patient has a non-missing baseline ADA result, and at least 1 non-missing postbaseline.

TE ADA positive (TE ADA+) patient: A patient who is evaluable for TE ADA is TE ADA+ if either of the following holds:

- **Treatment-induced:** The patient has baseline status of ADA Not Present and at least one postbaseline status of ADA Present with titer ≥ 20 (that is, 2^*MRD where for this ADA assay the MRD, the minimum required dilution of the ADA assay, is 10).
- **Treatment-boosted:** The patient has baseline and postbaseline status of ADA Present, with the postbaseline titer being 2 dilutions (4-fold) greater than the baseline titer. That is, the patient has baseline status of ADA Present, with titer 1:B, and at least one postbaseline status of ADA Present, with titer 1:P, with P/B ≥ 4 .

TE ADA Inconclusive patient: A patient who is evaluable for TE ADA is TE ADA Inconclusive if $\geq 20\%$ of the patient's postbaseline samples, drawn pre-dose, are ADA Inconclusive and the patient is not otherwise TE ADA+.

TE ADA negative (TE ADA-) patient: A patient who is evaluable for TE ADA is TE ADA- when the patient is not TE ADA+ and the patient is not TE ADA Inconclusive.

5.5.9.1.6.3. Analyses to be Performed

To evaluate the changes in immunogenicity data (Anti-GMB [ADA and NAb]) after treatment, the number and proportion of patients who are TE ADA+ will be tabulated where proportions are relative to the number of patients who are TE ADA evaluable as defined in Section 5.5.9.1.6.2). The baseline and postbaseline definitions for each analysis period are shown in Table CGAM.5.3. In detail the following statistical analyses for each immunogenicity analyte (ADA and Nab) are planned:

- the incidence of TE ADA will be summarized as following:
 - for safety population during double-blind treatment phase and compared between treatment arms using Fisher's exact test
 - for GMB-treated population during GMB-treated time

- for the ADA follow-up cohort during GMB-treated time; the ADA Follow-up Cohort is defined as patients in the GMB-treated population with ADA assessment during post-treatment phase
- for the ADA follow-up cohort during GMB-treated time and post-treatment phase combined
- shift from baseline to maximum post-baseline ADA titers for the GMB-treated population during GMB-treated time
- summary of time to first TE ADA+ titer during double-blind phase

The following descriptive listings will also be provided:

- listing of patients with TE ADA at any time during study, NAb status will also be displayed
- listing of patients with inconclusive ADA or inconclusive NAb at any time
- listing of patients with ADA present at any time or TE hypersensitivity events or TEAEs related to injection sites.

5.5.9.2. Continuous Safety Measures

Analyses of continuous safety data will be conducted on patients who have a baseline and at least one postbaseline observation for SP III.

For all the continuous safety measures (including planned laboratory measures, vital signs and weight, ECG intervals and heart rate), box-whisker plots with summary statistic tables for absolute value and change from baseline at scheduled visits and at endpoint (defined as the final post-baseline value) will be provided for SP III. The change from baseline results will be compared between treatment arms using the analysis of covariance (ANCOVA) model with treatment, pooled investigative site and baseline value in the model.

5.5.10. Subgroup Analyses

Subgroup analyses will be performed for primary efficacy measure (change from baseline on weekly number of cluster headache attack) only for the ITT patients in the SP III.

Table CGAM.5.10 provides definitions for each subgroup variable. Subgroup variables are usually selected if they are potentially prognostic or predictive. A subgroup variable is prognostic if values of the subgroup variable predict the change in efficacy measures regardless of the treatment group assignment. A subgroup variable is predictive if values of the subgroup variable predict heterogeneous treatment effect. Demographic subgroup variables (sex, racial origin, ethnicity, age, and region) may neither be prognostic nor predictive, but they are standard subgroup variables needed for regulatory submission. Baseline average daily number of cluster headache attack category, baseline verapamil use, and sex were included in the dynamic allocation randomization algorithm and are considered possibly prognostic. CCI

[REDACTED] The purpose of the analyses for these subgroup variables is to assess the consistency of treatment effects across the different values of each subgroup variable.

Table CGAM.5.11 summarizes the subgroup analyses to be conducted, using those subgroup variables presented in Table CGAM.5.10.

Table CGAM.5.10. Definition of Subgroup Variables

Subgroup Variable	Categories
1. Sex	Male, female
2. Racial origin (combine those with less than 10%)	American Indian / Alaskan Native Asian Black / African American Native Hawaiian / Pacific Islander White Multiple
3. Ethnicity	Hispanic or Latino Not Hispanic or Latino
4. Age	<40 or ≥ 40
5. Baseline average daily number of cluster headache attack category	1) ≤ 4 attacks per day, >4 attacks per day 2) ≤ 3 attacks per day, >3 attacks per day 3) ≤ 2 attacks per day, >2 attacks per day
6. Baseline verapamil use	Yes, No
7. Region	Europe, North America (US and Canada)
8. CCI	[REDACTED]

Table CGAM.5.11. Subgroup Analyses

Outcome Variable	Subgroup Variables	Analysis
EFFICACY VARIABLE		
1. Change from baseline to each postbaseline biweekly interval in the SP III for: Number of cluster headache attacks	
 • Sex • Racial origin • Ethnicity • Age • Baseline average daily number of cluster headache attack category • Baseline verapamil use • Region C CCI [REDACTED]	Repeated measures analysis using the model described in Section 5.5.8.1 with additional terms for subgroup, subgroup-by-treatment, subgroup-by-week, and subgroup-by-treatment-by-week interactions added to the base model.

Abbreviations: CCI [REDACTED]

SP = study phase.

For the subgroup variable of race, all the categories that have less than 10% of the patients in the study will be combined in the analysis. CCI [REDACTED]

[REDACTED] For subgroup analyses, the subgroup-by-treatment and subgroup-by-treatment-by-visit/week interactions will be tested at a

2-sided 0.05 significance level. Treatment group differences will be evaluated within each category of the subgroup variable.

The subgroup analysis for change from baseline to each biweekly interval in number of cluster headache attacks will be conducted with repeated measures analysis. The same MMRM model as described in Section 5.5.8.1 will be used with additional terms of subgroup, subgroup-by-treatment, subgroup-by-week, and subgroup-by-treatment-by-week interactions added. In this analysis, the p-value for the subgroup-by-treatment, subgroup-by-week, and subgroup-by-treatment-by-week interactions will be reported.

For subgroup analysis, the LSMeans and LSMeans change estimate as well as the treatment comparisons within each subgroup will be analyze with the data within that specific subgroup only.

5.5.11. Sensitivity Analysis

Dynamic Allocation (Minimization) Assumption

A permutation test will be performed as a sensitivity analysis of the primary MMRM analysis to confirm the results of the asymptotic inference. The key features of the permutation test which will be employed are as follows:

- The patients' baseline covariates, responses, and enrollment order will be considered fixed.
- The sharp null hypothesis will be assumed (that is, responses to GMB and placebo will be assumed exactly equal).
- The exact minimization algorithm and exact site pooling algorithm will be used to generate the null distribution of the primary test statistic from the MMRM analysis.
- The p-value based on the generated null distribution (that is, permutation test p-value) will be obtained by comparing the observed test statistic value to the percentiles of the generated null distribution.

Explicitly, the p-value is derived from the permuted distribution of test statistics as follows. If the total number of permutations is m , and b of these permutations have a test statistic greater than or equal to the observed test statistic, z , then the permutation p-value, p^p is,

$$p^p = \frac{b + 1}{m + 1}$$

where m equals 100,000. As discussed in Phipson and Smith 2010, this is an upper bound on the estimated p-value. This method is used to generate the approximate null distribution. Note that the described permutation p-value calculation should be conducted such that a positive value for the test statistic should indicate a favorable treatment effect GMB 300 mg relative to placebo.

If the sample size is not increased based on the interim results, the permutation test will be performed on the combined data from the interim and post-interim assessments since the CHW procedure will not be applied. If the sample size is increased, then the permutation test will be

performed on patients before and after the interim analysis. These results will be combined using the CHW procedure. The details of computing CHW statistics for the permutation test is summarized in [Appendix 1](#).

Missing Data Assumption

Sensitivity analyses will be performed to assess the robustness of the primary analysis conclusions to deviations from MAR assumption. The approach for these analyses is to vary the assumptions of missing data for the primary analysis in a systematic way. Basically, the method will be to predict the missing outcomes and then add a value (denoted as Δ_A) to the predictions in the active treatment group and another value (denoted as Δ_P) to the predictions in the placebo treatment group, consistent with the sensitivity approach suggested in Permutt (2015). This procedure will be repeated multiple times for different values of (Δ_A, Δ_P) using the following steps:

1. Predict the missing outcomes for each treatment via multiple imputation based on observed primary endpoint and baseline values. Such imputation will be carried out using a Markov Chain Monte Carlo method with a Jeffreys prior via SAS® PROC MI. Thirty (30) such imputations will be created.
2. Add Δ_A to the imputed values for patients taking active treatment and Δ_P to the imputed values for patients taking placebo.
3. Conduct the primary analysis separately for each of the 30 imputations.
4. Combine the results of these analyses using Rubin's combining rules, as implemented in SAS® PROC MI ANALYZE.

The above steps will be repeated multiple times for different values of (Δ_A, Δ_P) with Δ_P ranging from (0, twice the absolute value of the mean value seen for placebo in the primary analysis) and Δ_A ranging from $(\Delta_P, \Delta_P + \text{absolute value of the mean treatment difference seen within the primary analysis})$. For example, if the mean change from baseline for placebo is -3.6 and the corresponding treatment difference is -1.5, then Δ_P would range from (0, 7.2) and Δ_A would range from $(\Delta_P, \Delta_P + 1.5)$.

Normality Assumption

To assess the robustness of the MMRM results to deviations from normality assumption, a sensitivity analysis for raw number of cluster headache attacks (total number of cluster headache attacks for each interval without imputing missing value and without normalization to 14-day period) will be conducted with a repeated measures negative binomial regression model fitted with SAS® PROC GLIMMIX. The model will include treatment, gender, pooled investigative site, bi-weekly time period (Weeks 1/2, 3/4, etc.), baseline verapamil use (yes or no) and treatment-by-time-period interaction, as well as the continuous fixed covariates of baseline value, and log (number of compliant days within each bi-weekly time period divided by 14) as the offset in the model. In case of non-convergence, pooled investigative site may be excluded from the model. Directional consistency of treatment effects from this model and the primary analysis MMRM model as specified in Section [5.5.8.1](#) will be examined.

In addition, as another form of sensitivity analysis, residuals from the primary analysis MMRM model will be examined and outliers identified. Consistency of results before and after removing patients with outlier residuals will be examined.

All sensitivity analyses discussed above will be using ITT population including pre- and post-interim 1 data.

Pre- and Post-interim Consistency Assessment

If the sample size is increased based on the interim analysis data, differences between pre and post interim 1 data for baseline variables and endpoints will be evaluated. Specifically, baseline patient characteristics as summarized in Section 5.5.4 will be summarized for pre and post interim data separately. In addition, change from baseline in weekly cluster headache attacks frequency using all pre and post interim 1 data combined will be analyzed with MMRM method as specified in Section 5.5.8.1 with the exception of adding a binary covariate of “pre and post interim 1 status” with value of 1 for pre interim 1 data, and value of 0 for post interim 1 data, and pre and post interim 1 status-by-treatment interaction.

CCI

CCI

[REDACTED]

[REDACTED]

[REDACTED]

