The aim of this study is to assess the safety and efficacy of LY2951742 300 mg administered every 30 days for the prevention of chronic cluster headache.

Clinical Protocol Synopsis: Study I5Q-MC-CGAM

Name of Investigational Product: LY2951742	
Title of Study: A Phase 3 Randomized, Double-Blind, Placebo-Controlled Study of LY2951742 with a Long-Term Open-Label Extension in Patients with Chronic Cluster Headache	
Number of Planned Patients/Subjects: Entered: 231 Enrolled/Randomized: Planned 162 Completed (SP III): 146	Phase of Development: 3
Length of Study: 30 months	
Estimated first patient visit: Jun 2015 Estimated last patient visit: Dec 2017	
Primary Objectives: The primary objective is to assess the efficacy of LY2951742 300 mg administered every 30 days compared with placebo in reducing the frequency of weekly cluster headache attacks in patients with chronic cluster headache. The primary outcome measure is the weekly cluster headache attack frequency. The primary endpoint is the overall mean change from baseline in weekly cluster headache attack frequency during the 12-week double-blind treatment phase with LY2951742 compared with placebo. The baseline cluster headache attack frequency is based on the last 14 days in the eligibility report (pre-randomization diary phase).	
Gated Objectives: 
• To assess the efficacy of LY2951742 300 mg compared with placebo in the estimated mean proportion of patients with a 50% or greater reduction from baseline in the weekly frequency of cluster headache attacks during the 12-week double-blind treatment phase.• To assess the efficacy of LY2951742 300 mg compared with placebo in the proportion of patients meeting sustained response through Week 12. For this analysis, sustained response is defined as a 50% or greater reduction in the weekly cluster headache attack frequency from baseline to Weeks 3/4 and maintained at Weeks 5/6, Weeks 7/8, Weeks 9/10, and Weeks 11/12.	

Other secondary objectives:

- To assess whether LY2951742 300 mg is superior to placebo on the following:
 - mean change in the weekly cluster headache attack frequency from baseline to each 2-week interval through Week 12
 - the proportion of patients with a 50% or greater reduction in the weekly cluster headache attack frequency from baseline at each 2-week interval through Week 12

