- During open-label phase, the data from first injection date to the day before second injection date of open-label phase will be considered as Weeks 13 through 16. The first injection date in open-label phase will be considered as Day 1, then Days 1 to 14 will be Weeks 13/14; Day 15 to the day before next injection date will be Weeks 15/16.

For each biweekly interval, the following missing data imputation method will be used:

- 1) If there are ≤ 7 days with non-missing answer to cluster headache attack frequency in the biweekly interval; or 2) the diary compliance rate is $\leq 50\%$, then the biweekly interval will be considered missing;
- Otherwise, 1) if there are ≥ 8 days with non-missing answer to cluster headache attack frequency in the biweekly interval; and 2) the diary compliance rate is $> 50\%$, then the average number of cluster headache attacks across the non-missing days will be used to impute the missing days. Furthermore, the total cluster headache attack frequency during the biweekly interval will be calculated as the average number of cluster headache attacks across non-missing days times the actual number of calendar days within each biweekly interval.

Then to estimate a weekly outcome of the total frequency for an efficacy measure from ePRO diary, the biweekly interval results will be adjusted to 7-day (weekly) interval by multiplying $\frac{x}{2}$, where “x” is the actual number of calendar days within each biweekly interval. The purpose of adjusting to weekly interval is to be able to report the outcome as weekly frequency. Lastly, the change from baseline to Weeks 1/2, 3/4, 5/6, 7/8, 9/10, 11/12, 13/14, and 15/16 will be derived.

An example of missing data imputation is described below in [Table CGAM.5.1](#).

Table CGAM.5.1. Example of Missing Data Imputation Outcome

	Example 1			Example 2		
	Number of Calendar Days	Number of Days with Non-Missing Answer to Cluster Headache Attack Frequency	Missing Data Imputation	Number of Calendar Days	Number of Days with Non-Missing Answer to Cluster Headache Attack Frequency	Missing Data Imputation
Weeks 1/2	14	14	*a	14	8	*b
Weeks 3/4	13	8	*b	13	7	*d
Weeks 5/6	14	6	*c and *d	14	14	*a
Weeks 7/8	17	8	*c	13	8	*b
Weeks 9/10	14	14	*a	14	14	*a
Weeks 11/12	13	6	*c and *d	16	8	*c

*a No imputation.

*b The average number of cluster headache attacks across the non-missing days will be used to impute the missing days.

*c Set to missing (diary compliance $\leq 50\%$).

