5.5.1. General Considerations

General aspects of statistical analyses are described below.

Unless otherwise specified, efficacy analyses will be conducted on an **intent-to-treat (ITT) population**, which include all patients who are randomized and receive at least one dose of study drug. Patients in the ITT population will be analyzed according to the treatment group that they were randomized to. Safety analyses for SP III will be conducted on the **safety population** which also includes all patients who are randomized and receive at least one dose of study drug. However, patients will be analyzed by actual study treatment received most often (modal treatment) during the double-blind treatment phase. Modal treatment will be the same as randomized treatment except in some cases of incorrect treatment administration. When mean change from baseline is assessed, the patient will be included in the analysis only if he/she has a baseline and a post-baseline measurement.

The additional analyses populations are described in [Table CGAM.5.2](#).

Safety analyses (Section [5.5.9](#)) and analyses for exposure will be conducted based on the modal treatment group patients have received (placebo or GMB300mg) during the double-blind treatment phase. For determining modal treatment, if there are 2 modes, then the modal treatment group will be GMB300mg.

Table CGAM.5.2. Study Phase, Analysis Population and Corresponding Treatment Groups

Study Phase (SP)	Analysis Population	Population Definition	Treatment Groups
SP III	ITT Population	All patients who are randomized and receive at least one dose of study drug	SP III treatment (based on randomization): Placebo, Galcanezumab 300mg (GMB300mg)
SP III and first 4 weeks of SP IV combined ^a			
SP III	Safety Population	All patients who are randomized and receive at least one dose of study drug	SP III treatment (based on modal treatment arm): Placebo, GMB300mg
SP IV	Open-label population	All patients who entered the open-label extension phase (SP IV) as indicated by receiving any injections in any open-label extension visit	SP III/IV treatment: Placebo-GMB300mg, GMB300mg-GMB300mg
SP III/IV Combined (GMB-treated time)	GMB-treated population	All patients who have exposure to Galcanezumab: 1) patients who received GMB300mg during SP III;	SP III/IV treatment: GMB300mg

Study Phase (SP)	Analysis Population	Population Definition	Treatment Groups

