5.5.1.2. Handling of Dropouts or Missing Data

Repeated measures analyses will be used as the statistical approach for handling missing data. The model parameters are simultaneously estimated using restricted likelihood estimation incorporating all of the observed data. Estimates have been shown to be unbiased when the missing data are missing at random and when there is ignorable non-random missing data (Mallinckrodt et al. 2008). Missing at random (MAR) assumption will be evaluated using sensitivity analyses as defined in Section 5.5.11.

Approaches for handling missing data for derivation of cluster headache attacks derived from ePRO per 14-day interval

In Study CGAM, for primary measure of cluster headache attacks, the daily data for each patient (including last 14 days in the eligibility report [pre-randomization diary phase], 12 weeks of daily data during double-blind treatment phase and 4 weeks of daily data during open-label extension phase) will be converted into 9 roughly 14-calendar day intervals: the baseline 14-day interval(baseline), Weeks 1/2, 3/4, 5/6, 7/8, 9/10, 11/12, 13/14, and 15/16. Each day, the patient may have zero, one, or multiple cluster headache attacks. For each biweekly interval, the following missing data imputation method will be used:

- 1) If there are ≤ 7 days with non-missing answer to cluster headache attack frequency in the biweekly interval; or 2) the diary compliance rate is $\leq 50\%$, then the biweekly interval will be considered missing;
- Otherwise, 1) if there are ≥ 8 days with non-missing answer to cluster headache attack frequency in the biweekly interval; and 2) the diary compliance rate is $> 50\%$, then the average number of cluster headache attacks across the non-missing days will be used to impute the missing days.

For detailed example about missing data imputation, please see Section 5.4.1.2.

Then the change from baseline to Weeks 1/2, 3/4, 5/6, 7/8, 9/10, and 11/12 will be derived.

The same approach will also be applied to secondary and exploratory efficacy measures that derived from ePRO data.

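### With the same dropout pattern in both arms, the SAP 5.5.11 missing-data grid stops where missing drug intervals equal missing placebo intervals; it is not run to a tipping point

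*SAP*

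**What the plan says.** SAP 5.5.1.2 handles missing data through the repeated measures model and passes the check of its main assumption elsewhere: "Missing at random (MAR) assumption will be evaluated using sensitivity analyses as defined in Section 5.5.11". SAP 5.5.11 takes this up: "Sensitivity analyses will be performed to assess the robustness of the primary analysis conclusions to deviations from MAR assumption".

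The first step is "Predict the missing outcomes for each treatment via multiple imputation based on observed primary endpoint and baseline values". Delta_A is then added to imputed drug values and Delta_P to imputed placebo values, the primary analysis is run on each of 30 imputations, and the results are combined by Rubin's rules. Delta_P runs from 0 to twice the absolute placebo mean. Delta_A runs from Delta_P to Delta_P plus the "absolute value of the mean treatment difference seen within the primary analysis". The worked example supposes "if the mean change from baseline for placebo is -3.6 and the corresponding treatment difference is -1.5", which gives Delta_P up to 7.2 and Delta_A up to Delta_P + 1.5.

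Missing data arise from early discontinuation and from the diary rule in SAP 5.4.1.2. Under that rule, if 7 or fewer days are answered or compliance is 50% or lower, "then the biweekly interval will be considered missing". The public text gives no other departure-from-MAR analysis for the primary endpoint, and no instruction to extend the grid until significance is lost.

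**The concern.** A sensitivity analysis of this kind should show how bad the missing drug data would have to be before the conclusion fails. This grid has a preset stop tied to the observed effect, so a smaller effect gets a smaller stress test. A report could say that the result held at every grid point although one asymmetric assumption just outside the grid would overturn it. The reverse also applies: a sturdy result cannot show how sturdy it is.

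Asymmetric assumptions are worth examining here. Protocol 8.4.3 requires discontinuation before a non-allowed preventive is started. Protocol 10.1.1 provides for diary recording in SP II, SP III and SP IV to Visit 11, and the SP V schedule lists no diary review. Some missing intervals may therefore follow treatment failure.

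**Working it through.** **Inputs from the documents.** Example placebo change -3.6 and difference d = -1.5 (SAP 5.5.11, illustrative). Planned numbers: "Planned 162 Completed (SP III): 146" (Protocol Synopsis), randomized 1:1 (SAP 5.3). That is 81 per arm and 162 - 146 = 16 non-completers (9.9%).

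**Assumptions.** The SD and the split of non-completers by arm are not public. Each non-completer is assumed to have at least one observed interval, because SAP 5.5.1 says "the patient will be included in the analysis only if he/she has a baseline and a post-baseline measurement". The last observed interval is spread evenly over intervals 1 to 5, so on average (5+4+3+2+1)/5 = 3 of 6 intervals are missing. The missing share is 16 × 3 / (162 × 6) = 48/972 = 4.9%.

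**Step 1: reproduce the SAP's grid.** 2 × 3.6 = 7.2 and |-1.5| = 1.5, so the largest Delta_A is 7.2 + 1.5 = 8.7. This agrees with the SAP.

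**Step 2: gap among missing intervals.** Gap (drug minus placebo) = MAR-predicted gap + (Delta_A - Delta_P). If the MAR-predicted gap is about d = -1.5:

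| Delta_P | Delta_A | Missing placebo mean | Missing drug mean | Gap |
|---|---|---|---|---|
| 0 | 1.5 (cap) | -3.6 | -3.6 | 0 |
| 3.6 | 5.1 (cap) | 0 | 0 | 0 |
| 7.2 | 8.7 (cap) | +3.6 | +3.6 | 0 |
| 0 | 5.1 (outside grid) | -3.6 | 0 | +3.6 |

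The last row is drug-only return to baseline. The premise was checked by large-sample simulation (10% dropout, correlation 0.7, SD 5 to 10). With the same dropout rule in both arms and a constant effect, the gap at the cap was -0.09 to +0.12. With an effect growing over time (SD 7) it was -0.42 to -0.22, still in favour of drug.

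**Step 3: overall estimate.** Difference = d + fA × Delta_A - fP × Delta_P, where f is the missing share in each arm. With equal f at the cap this is d(1 - f) for any Delta_P: -1.43 at 4.9%, -1.35 at 9.9%, -1.20 at 20%. For (5.1, 0) with 8 non-completers per arm, f = 8 × 3 / (81 × 6) = 0.049 and the estimate is -1.5 + 0.049 × 5.1 = -1.25.

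**Step 4: p values with the SE held fixed, 8 v 8** (two-sided, so 0.05 matches the SAP's one-sided 0.025).
- Starting p 0.025 (z = 2.241). Cap: 2.241 × 0.951 = 2.131, p = 0.033. Drug-only return: 2.241 × 1.25/1.5 = 1.87, p = 0.06.
- Starting p 0.01 (z = 2.576). Cap: 2.576 × 0.951 = 2.449, p = 0.014. Drug-only return: 2.576 × 1.25/1.5 = 2.15, p = 0.03.

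**Step 5: simulation, which also lets the SE grow with the shifts.** Six intervals, within-patient correlation 0.6, response-independent dropout, constant effect, 30 proper imputations per arm, t test on patient means without covariates, Rubin's rules. Each data set was scaled so that (0, 0) gives -1.5 and exactly the starting p. Medians over 300 runs, drug v placebo non-completers:

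| Starting p | Quantity | 6 v 10 | 8 v 8 | 10 v 6 |
|---|---|---|---|---|
| 0.01 | Largest p on SAP grid | 0.013 | 0.021 | 0.047 |
| 0.01 | p at (5.1, 0) | 0.025 | 0.034 | 0.044 |
| 0.01 | Tipping Delta_A at Delta_P = 0 | 9.2 | 6.8 | 5.6 |
| 0.025 | Largest p on SAP grid | 0.031 | 0.042 | 0.080 |
| 0.025 | p at (5.1, 0) | 0.050 | 0.065 | 0.079 |
| 0.025 | Tipping Delta_A at Delta_P = 0 | 5.1 | 3.7 | 3.0 |

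The SAP's cap at Delta_P = 0 is 1.5. At 8 v 8 and starting p 0.025, the whole grid stayed below 0.05 while (5.1, 0) did not in 65% of runs; separate simulations under the same assumptions gave 50% and about 60%. At starting p 0.01 the share was 2%. Correlations of 0.3 and 0.8 moved p by no more than 0.003. If missingness were doubled, for instance by diary non-compliance (a rate the documents do not give), 16 v 16 with starting p 0.01 gives 0.037 on the grid against 0.093 at (5.1, 0).

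**The case against.** The grid is pre-specified and not empty. At its relative limit the drug has no advantage in missing intervals, and it covers both arms returning to baseline and both worsening. Nothing in the SAP promises a tipping-point search, and SAP 5.5.1 already allows further exploratory analyses. All of this stands, though permission to explore does not commit anyone to the missing runs.

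A reader might infer that similar dropout rates are enough for the grid never to reach missing drug intervals worse than placebo. The documents do not support that. Imputation is done by treatment from patients' observed data, so if poor responders leave drug selectively, the imputed drug values are already poor. In simulation with equal 10% rates but dropout tied more strongly to poor response on drug, missing drug intervals at the cap were 2.2 to 4.5 attacks per week worse than placebo.

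A reader might also infer that only runs at Delta_P = 0 are informative. That fails too. When drug has at least as much missing data, the high-Delta_P corner is the harshest existing point: at 10 v 6 and starting p 0.01, p is about 0.045 at (8.7, 7.2) against 0.016 at (1.5, 0). Only when placebo has more missing data does raising Delta_P move the estimate in the drug's favour (at 6 v 10, -1.63 at (8.7, 7.2)).

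The hidden-reversal window is narrow: at 8 v 8, starting p between about 0.0175 and 0.032. Drug-only return to baseline is a benchmark that the documents give no particular reason to expect. Non-responder imputation for sustained response (SAP 5.5.8.2) offers partial cover, but for another endpoint and in both arms alike.

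**Conclusion.** The point holds as a minor one. With the same dropout mechanism, timing and rate in both arms and a roughly constant effect, the grid's worst relative case is no drug benefit in missing intervals. It then does not test missing drug intervals being worse, and its reach shrinks with the observed effect.

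The gap matters for moderately significant results: at 8 v 8 and starting p 0.025, about 0.04 on the grid against about 0.065 outside it. It does not change the reading at starting p 0.01 with about 5% of intervals missing. At 10 v 6 the existing grid is about as harsh as the omitted case and already shows any fragility. These figures rest on the SAP's illustrative effect, an assumed arm split, evenly spread dropout and a simplified model.

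It would be wrong to infer that the primary result is at risk: the analysis is supportive, and primary inference and type I error do not depend on it.

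**What to change.** Keep the multiple imputation and the entire existing grid, including the high-Delta_P runs. Add to SAP 5.5.11 runs that vary Delta_A independently of Delta_P, across the Delta_P range including 0, and beyond Delta_P plus the absolute difference, until the primary conclusion is lost. Report the resulting tipping boundary with the fraction of missing biweekly intervals in each arm and a judgement of whether shifts of that size are plausible.

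The cost is one SAP paragraph and a few more runs of the same program; the primary test is untouched. The downside is that a fragile result may be displayed as such.
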